We have a dissemination plan specific to our project “He Tapu Te Whare Tangata”. Our goal is to improve outcomes and this requires our partnership (researchers, community and primary care) having ongoing consultation with multiple groups. Our priority for the dissemination of results will be firstly the community and Māori health organisations and strategic organisations that have been part of the research process. Maintaining the link between academia and Māori communities is part of our commitment to ongoing consultation and dissemination. Dissemination and consultation with the clinical workforce, health services (DHBs) and policy makers is a priority to inform about results and to bring about change. Importantly we will have ongoing consultation with the National Screening Unit with the goal that this community intervention if successful will directly inform the future changes to the National Cervical Screening Program to prioritise Māori and lead to a program

that meets the needs of Māori. [name] (PI) is on the Technical Advisory Group for the introduction of the NZ primary HPV testing program. She is a previous member of the National

Kaitiaki Group and the Māori Equity Advisory Group for the introduction of the HPV vaccine into NZ.

We have established multidisciplinary clinical networks in all 20 DHBs that are keen to be involved in receiving this knowledge and in change management activities. Multiple opportunities will be taken to disseminate results at a range of Māori health and other hui such as: Māori health provider Board and staff hui, and Marae committees. At a regional and central level, our focus is to achieve change and influence policy and practice hui may include: Māori Women's Welfare League, National Kaitiaki group, workshops, educational courses, policy groups, advisory committees, Te Ora, Ngā Neehi Māori, He Hono Wahine etc. In addition, we plan to publish our findings in high ranked peer review publications and presentations at indigenous forums to share and learn.

Conflict of interest statement

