Pathway 1 is HPV self-test with onsite POC results within one hour paired with kanohi ki te kanohi (face to face) information, support and immediate appointments for a secondary service for those who are HPV positive.

Pathway 2 is HPV self-test with swab sent to laboratory, and the usual result giving, information and support, and usual referral pathways for those who are HPV positive.

Hypothesis

We hypothesise that **Pathway 1** will improve timely diagnosis and treatment access for women, compared to **Pathway 2**.

This is a cluster crossover intervention trial, with communities (study sites) as clusters. The two rural North Island communities (Te Wairoa, Ngāti Porou rohe of Tairāwhiti) will be randomised to either starting with Pathway 1 or Pathway 2 and then crossing to the other pathway after 15 months for the second period of the study. The trial governance will be led by Ngāti Pāhauwera with Tipu Whaipua (Te Wairoa steering committee) and Ngāti Porou Hauora.

Women in both pathways will be offered a HPV self-test as the HPV self-test is acceptable for Māori and is likely to be gold standard when the new HPV primary testing programme commences in NZ.

Study Objectives

1. To compare a community controlled innovative cervical cancer prevention care pathway with usual referral pathway to examine whether timely access to screening, diagnosis and treatment can be improved. (quantitative).
2. To assess acceptability and feasibility of community control of the care pathways (qualitative).

Ethics

Approval from the National Health and Disabilities Ethics Committee (HDEC) was given in Dec 2020 (20/NTB/311), the Hawkes Bay DHB and Tairāwhiti NPH locality were approved Feb 2021 which includes Māori directorates.

The Ngāti Porou Hauora Board also approved for the project to proceed with NPH primary care service and eligible patients.

The Wairoa directors and board have approved for the project to proceed in the Wairoa (Queens Street Practice) primary care service and eligible patients.

Kaupapa Māori Research Methodology

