
One site will start on Pathway 1 and the other site will start on Pathway 2. After 15 months the Pathways will then cross over for the second 15 month period recruitment so each site will experience each pathway over the 30 months of the study. NB this timeline has been extended see Page 19
	
Pathway 1	Pathway 2

POCResults in 1 hour
 	
Test swab to off-site lab

Immediate on-site result to patient with information and support HPV negative information given with follow up screening times
	
Results to GP/Nurse

Immediate referral date for colposcopy if HPV positive
	
Patient notified by text or phone HPV negative information given with follow up screening times

Colposcopy
	
Letter/ phone/ text to patient if positive Letter of referral to gynaecologist Outpatient appointment generated & sent to patient

	
Colposcopy

Primary Outcome- Pathway 1 vs Pathway 2

Proportion of women with an HPV positive test having a colposcopy within 20 working days (MOH Indicator) of referral

Secondary Outcomes: Pathway 1 vs Pathway 2

Proportion of women with an HPV positive test having a colposcopy within 40 days of referral (MOH indicator)

1. Time from test to patient notification of results (positive or negative)
2. Time from test and time from receiving results to treatment for women with positive results/high grade histology

For both groups: (Intervention and Control)

3. Numbers of HPV positive, HPV negative results and invalid results
4. Numbers of high grade lesions (CIN2 CIN3, Carcinoma)
5. Proportion of under-screened / never screened women receiving test and follow up

Training

Both sites' doctors, nurses, kaiāwhina and research assistant will receive an HPV update and information sharing session with experts in the research team before recruitment of women starts. These updates will include the role of HPV in cervical cancer, the HPV self-test, the potential role of POC testing, how to get informed consent, how to instruct women on taking a self-taken swab, following up results, the role of the research team and how the study will run.

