The order of treatment for each practice will be randomly allocated by the study statistician using computer generated random numbers.

Sample size

The primary outcome is the proportion of women having a colposcopy within 20 working days from referral, for those women with a positive HPV test result. The target communities are predominantly Māori women in a rural setting. Based on the latest percentage reported for Māori women throughout New Zealand, we assume that 56.4% of women in the control arm will have a colposcopy within 20 working days following referral for a positive HPV test (ref). We aim to detect a 50% increase (RR=1.5) from 56.4% to 84% in the primary outcome for the intervention arm. A sample size of 80 women (40 in each arm) in a two-period, two-cluster randomised crossover trial will give 80% power at 2-sided alpha of 0.05 to detect a 50% increase in the intervention arm. With only 2 practices serving as the clusters, the sample size does not

account for the cluster effect which was considered as a fixed effect in the final analysis.

Analysis

All statistical analyses will be performed using SAS version 9.4 and R version 3.4.2. Analyses will be intention to treat and conducted at the individual participant level. All tests of significance were two-tailed and a 5% significance level throughout the analyses. Continuous variables were compared with t-tests or Mann-Whitney tests and categorical data with chi-squared tests as appropriate.

A generalised linear regression model with a binomial distribution and logit link will be used to analyse binary outcomes, and a linear regression model will be used to analyse continuous outcomes, with treatment and period fitted as fixed effects. For the primary outcome both unadjusted and adjusted analyses for potential covariates measured at baseline will be conducted. Time to notification and time to colposcopy will be analysed using Kaplan-Meier curves, log rank test and Cox proportional hazard models.

Data safety and monitoring

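### The Analysis section fits only treatment and period, although the Sample size section relies on cluster being a fixed effect; as written, the primary model is exposed to bias from site differences if accrual shifts between periods

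*Protocol*

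**What the plan says.** The design is given under Hypothesis in the Methodology: "This is a cluster crossover intervention trial, with communities (study sites) as clusters". Table 1 sets the order: "One site will start on Pathway 1 and the other site will start on Pathway 2", with a cross-over for the second period.

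The Sample size section plans for "A sample size of 80 women (40 in each arm) in a two-period, two-cluster randomised crossover trial". Pointing to there being just two clusters, it says that this number makes no attempt to "account for the cluster effect which was considered as a fixed effect in the final analysis".

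The Analysis section, which follows directly, specifies a binomial-logit model for binary outcomes and a linear model for continuous ones, "with treatment and period fitted as fixed effects". Site is not in that list. Unadjusted and covariate-adjusted versions of the primary analysis are both planned, but the baseline covariates are not named.

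**The concern.** In a two-site, two-period crossover, the site term is what makes the pathway comparison a within-community one. The sample-size argument leans on that term, and the model sentence leaves it out. An analyst who follows the Analysis section literally fits a different primary model from one who follows the Sample size section.

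This matters because the two communities are served by different DHB gynaecology services (Colposcopy section), and the primary outcome is how soon those services see a referred woman. If timeliness differs between them and accrual shifts between periods, part of that difference is reported as a pathway effect.

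**Working it through.** **The plan's own figure.** Inputs from the Sample size section: "we assume that 56.4% of women in the control arm will have a colposcopy within 20 working days"; "We aim to detect a 50% increase (RR=1.5) from 56.4% to 84% in the primary outcome"; 80% power; two-sided alpha 0.05. A two-proportion formula with pooled variance and no continuity correction gives 40 per arm for 56.4% against 84.6% (1.5 × 56.4%), with power 80.1%. With the rounded 84% it gives 42 per arm, and power at 40 per arm is 78.1%. The stated 80 women is reproduced, so the problem is the model and not the arithmetic of N.

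**Bias without site.** Let site A start on Pathway 1, let δ be the pathway effect and s the outcome difference A − B.

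- Period 1: A on Pathway 1 minus B on Pathway 2 = δ + s.
- Period 2: B on Pathway 1 minus A on Pathway 2 = δ − s.
- A linear model with treatment and period weights these by w = nA·nB/(nA + nB) in each period, so bias = s × (w1 − w2)/(w1 + w2).

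The share that leaks, by recruitment at each site:

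- 22 then 18 at both sites: w = 11 and 9; 2/20 = 0.10.
- 25 then 15 at both: w = 12.5 and 7.5; 5/20 = 0.25.
- 30 then 10 at both: w = 15 and 5; 10/20 = 0.50.
- A 30 then 30, B 10 then 10: w = 7.5 and 7.5; 0.
- A 30 then 10, B 10 then 30: w = 7.5 and 7.5; 0.

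**Size on the odds-ratio scale.** The protocol gives neither site rates nor cell counts, so both are assumptions: 80 women, no pathway effect, sites at 66% and 46% (20-point gap) or 61% and 51% (10-point gap), better site starting on Pathway 1. Logistic fits to simulated cells, likelihood-ratio test at 5%, without site:

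| Split at both sites | Gap | Odds ratio | False-positive rate |
|---|---|---|---|
| 22/18 | 20 points | about 1.1 | about 5% |
| 25/15 | 20 points | 1.23 | about 7% |
| 30/10 | 20 points | 1.5 | about 15% |
| 25/15 | 10 points | 1.11 | about 6% |
| 30/10 | 10 points | 1.23 | about 8% |

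If the better site starts on Pathway 2, the direction reverses: 30/10 with a 20-point gap gives 0.66. With site in the model, the expected odds ratio is 1.00 in every row and the likelihood-ratio false-positive rate is about 6%.

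**Under the planned effect.** The design odds ratio is (0.84/0.16)/(0.564/0.436) = 4.06. With a 20-point gap and no site term, it is estimated as 5.42 at 28/12 and 2.83 at 12/28. With equal cells it is only mildly attenuated, to 3.89.

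**Power cost of adding site** (84% against 56.4%, no site gap, likelihood-ratio test): about 80% with 20 per cell, 78% at 25/15 and 69% at 30/10, against about 80% without site. A Wald test loses more. With equal cells it falls from about 78% to between 72% and 77%, depending on how samples with all events in one cell are handled. At 30/10 it falls to about 50%.

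**The case against.** The strongest reply is that site is already in the plan. The Sample size section says so, and the natural joint reading is treatment, period and cluster, with an incomplete list in the next section. That is fair as a guess at intent, and a reader who concludes that the protocol has abandoned site adjustment, or that the benefit of crossing over is lost, goes too far. But the sentence that defines the model is the one an analyst will follow, and the unnamed baseline covariates do not supply the term.

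Second, a reader might infer that unequal accrual is likely. The protocol does not support that. Under Cohort lists, the under-screened list is fixed beforehand, and half of those women are offered the test in each year. The amended timeline gives periods of similar length. Imbalance is only possible: the halving covers offers to under-screened women, all women due a screen may join, and the second period runs for up to 15 months. Near the planned balance (22/18) the false-positive rate barely changes, at 5.3% without site and 5.6% with it.

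Third, it is tempting to say that all four cells must balance. They need not. Sites of different size cause no bias under the null if their sizes stay constant over the periods.

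Finally, nothing makes the generic chi-squared sentence the primary pathway test, since binary outcomes are assigned to the regression model. Details of the log-rank and Cox analyses may properly sit in an SAP.

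**Conclusion.** The inconsistency is on the face of the protocol and does not depend on an unseen SAP: the model sentence omits a term that the sample-size justification says the final analysis contains. It should be corrected before analysis.

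The consequence is conditional. It needs both a site difference in the outcome and a shift in accrual that makes w1 differ from w2. Under the assumptions above, the effect on the false-positive rate runs from negligible (22/18) to about 15% (30/10 with a 20-point gap). The larger figures are illustrations and not forecasts, because the protocol gives no site rates or cell counts.

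A reader might also infer that adding site costs no power or fully protects the comparison. Neither is so. Power is about unchanged only with balanced cells. Treatment, period and site together also use all the information in the four site-period cells, so any change over time that differs between the sites stays inseparable from the pathway effect.

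**What to change.** In the Analysis section, list treatment, period and site as the fixed effects for the binary and continuous outcomes, and state that this is the primary model. This brings it into line with the Sample size section. Carry site and period into the Cox models in the same way, for example by stratifying on site and including period as a covariate. State as a limitation that site-by-period changes cannot be separated from the pathway effect with two clusters.

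The cost is one sentence, one degree of freedom and the loss of power shown above if accrual is uneven. The choice of test can be left to the SAP, but it should be fixed in advance, because a Wald test gives up more power than a likelihood-ratio test when cells are small.
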